5.8.3 Key Secondary Efficacy Endpoint

OS is designated as a key secondary endpoint. The key secondary endpoint will be tested at a 1-sided 0.025 level when the test of mPFS is statistically significant.

OS is defined as the time from the date of randomization to the date of death. Patients without documented death at the time of analysis will be censored at the date last known to be alive.

There will be 2 formal analyses for OS, an OS interim analysis at the time of the final mPFS analysis, and the OS final analysis when 112 deaths have occurred. Overall type I error will be controlled using the O'Brien-Fleming method with a Lan-DeMets alpha spending function.

Brentuximab vedotin (ADCETRIS™)
Statistical Analysis Plan, Study C25003

Stratified log-rank testing will be used to compare OS between the 2 treatment arms. The stratification factors include region and number of IPFP risk factors at baseline (Section 5.2). The hazard ratios along with the 95% CIs (2-sided) will be estimated using a stratified Cox regression model. The Kaplan-Meier method will be used to estimate the distribution of the OS endpoint for each treatment. The 25th, 50th (median), 75th percentiles of survival times (if estimable), and the 2-sided 95% CIs will be presented. Analysis of OS will be performed based on the ITT population.

In addition, a stratified Cox regression model will be used to further evaluate the treatment effects on OS after adjusting for some prognostic factors. Besides treatment and the stratification factors (Section 5.2), the following prognostic factors will be included in the model simultaneously: age, race (white, non-white), baseline ECOG score, baseline cancer stage, baseline B symptoms, and PET results from Cycle 2. Additional exploratory analyses may be performed if deemed necessary.

Subgroup analyses may be performed using subgroups defined for mPFS analyses. Additional analyses of OS may be performed if deemed necessary.

5.8.4 Other Secondary Efficacy Endpoints

5.8.4.1 Overview of Statistical methods

Other secondary efficacy endpoints mainly consist of 2 types of variables: time to event variables (eg, event-free survival) and binary outcome variables (eg, CR). For time to event variables, the statistical methods will be the same as that for time to death outlined in Section 5.8.3. For binary outcome variables, the statistical methods will be the same as that for CR outlined in Section 5.8.4.2. Other endpoints that don't belong to these 2 categories will be addressed separately.

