### **2.2 Secondary Objectives**

The key secondary objective is

- To determine if A+AVD improves OS versus that obtained with ABVD

Other secondary objectives are:

- To determine if A+AVD improves CR rate versus that obtained with ABVD
- To determine the safety profile of A+AVD relative to that of ABVD
- To determine the event-free survival (EFS) obtained with A+AVD and ABVD
- To determine the disease-free survival (DFS) rate obtained with A+AVD and ABVD
- To determine if A+AVD improves overall ORR (defined as CR + PR) versus that obtained with ABVD
- To determine the DOR and duration of complete remission (DOCR) obtained in the A+AVD and ABVD arms
- To determine the rate of patients receiving irradiation for HL not in CR in the A+AVD and ABVD arms
- To determine the rate of patients in CR at the end of frontline therapy in the A+AVD and ABVD arms
- To determine the rate of Cycle 2 PET negativity in patients treated with A+AVD versus those treated with ABVD
- To determine if A+AVD improves health-related quality of life (HRQOL) versus ABVD

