## **Brentuximab vedotin (ADCETRIS®)**

### **Clinical Study Protocol C25003 Amendment 7, EudraCT: 2011-005450-60**

between the 2 treatments will also be provided. ORR per IRF will be analyzed based on the ITT population.

Similar analyses will be conducted to compare the rate of patients that received consolidating irradiation between the 2 treatment arms.

CR rate at the end of frontline therapy will be assessed similarly to CR rate at the end of treatment with randomized regimen.

DOR in subjects with confirmed response is the time between first documentation of response and disease progression. DOCR in subjects with confirmed CR is the time between first documentation of CR and disease progression. DOR and DOCR per IRF will be analyzed based on the ITT population.

EFS is defined as the time from randomization until any cause of treatment failure: disease progression, premature discontinuation of treatment for any reason, or death due to any cause, whichever occurs first. Analyses of EFS will be performed based on the ITT population.

DFS is defined as the time from CR to disease progression or to death from lymphoma or acute toxicity from treatment. Analyses of DFS will be performed based on the subset of the ITT population achieving a CR.

The same analyses will be applied to these time-to-event endpoints as those described for OS above.

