5.8.4.5 Disease-Free Survival

DFS is defined as the time from CR to disease progression or to death from lymphoma or acute toxicity from treatment. Analyses of DFS will be performed based on the subset of the ITT population achieving a CR. DFS is a time-to-event variable.

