5.8.4.7 Duration of Response (DOR) or Complete Response (DOCR)

DOR in subjects with confirmed response is the time between first documentation of response (PR or CR) and disease progression. DOCR in subjects with confirmed CR is the time between first documentation of CR and disease progression. DOR and DOCR per IRF will be analyzed based on the subset of ITT population who had response. DOR and DOCR are time-to event-variables.

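### DOR, DOCR and DFS are compared between arms by log-rank test and hazard ratio in post-randomization responder subsets, which can hide or create a difference if response rates differ by arm

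*SAP*

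**What the plan says.** SAP 5.8.4.1 assigns one method to every other secondary time-to-event endpoint: "For time to event variables, the statistical methods will be the same as that for time to death outlined in Section 5.8.3". SAP 5.8.3 supplies that method: "Stratified log-rank testing will be used to compare OS between the 2 treatment arms", and "The hazard ratios along with the 95% CIs (2-sided) will be estimated using a stratified Cox regression model". It adds a covariate-adjusted Cox model, described as evaluating treatment effects, and Kaplan-Meier estimation by arm.

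The analysis sets are narrower than for OS. For DFS, SAP 5.8.4.5 says: "Analyses of DFS will be performed based on the subset of the ITT population achieving a CR". For the durations, SAP 5.8.4.7 says: "DOR and DOCR per IRF will be analyzed based on the subset of ITT population who had response". It then classes them so that the OS method applies: "DOR and DOCR are time-to event-variables". SAP 5.8.4.5 classes DFS the same way.

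Protocol 8.1.6.2 also carries the OS analyses over to DOR, DOCR, EFS and DFS. SAP 3.1 says that hypotheses for the secondary endpoints will be tested. Neither document calls the responder-only comparisons descriptive or plans an analysis that deals with selection into the subset.

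**The concern.** Response is an outcome of treatment. Once the comparison is confined to responders, randomization no longer makes the two groups comparable. Raising the CR rate is a stated objective (SAP 1.2). If A+AVD succeeds, its CR subset contains patients whose counterparts on ABVD are left out. If those extra patients relapse more often, A+AVD durability looks worse than it is in patients who would have responded on either regimen. If their prognosis is better, the shift goes the other way.

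The adjusted Cox model does not settle this. Baseline covariates cannot guarantee balance in a subset defined after treatment, and the model also includes the Cycle 2 PET result, itself measured after randomization.

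What is at stake is how three supporting endpoints are read: a p-value or hazard ratio for durability could be taken as a randomized treatment effect.

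**Working it through.** **Plan figures.** The documents give no event count, power or expected effect for DOR, DOCR or DFS, so there is no figure to reproduce for these endpoints. The one design figure at hand, 260 mPFS events for 90% power at HR 0.67 and 1-sided 0.025 (SAP 5.1), does reproduce: Schoenfeld's formula gives 263 events, and power at 260 is 0.898. The point does not depend on it.

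**Arithmetic illustration (all inputs assumed).** ABVD: 70% reach CR and 12% of them relapse. On A+AVD the same patients relapse at 0.67 × 12% = 8.04%, and a further 5% of all patients reach CR, with relapse risk r.

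Relapse in the A+AVD CR subset = (0.70 × 0.0804 + 0.05 × r) / 0.75. The apparent ratio is this divided by 0.12.

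- r = 0.20: (0.05628 + 0.010)/0.75 = 0.088; ratio 0.74
- r = 0.40: (0.05628 + 0.020)/0.75 = 0.102; ratio 0.85
- r = 0.50: (0.05628 + 0.025)/0.75 = 0.108; ratio 0.90

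The true ratio in shared responders is 0.67 throughout.

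**Simulation illustration (also assumed).** There are 620 patients per arm, 1,000 runs per scenario, and an unstratified log-rank test and Cox model in responders only. ABVD CR is 72%, the low end of the 72-90% range cited in protocol 1.4. Shared responders on ABVD are 85% relapse-free at 3 years, follow-up is 1.5 to 4.5 years, and dropout is 5% a year. Everyone who responds on ABVD is taken to respond on A+AVD as well. Extra A+AVD responders relapse at twice the ABVD shared-responder rate.

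| A+AVD CR | True HR 1.00: apparent HR | False finding against A+AVD (nominal 2.5%) | True HR 0.75: apparent HR | Chance of showing benefit |
|---|---|---|---|---|
| 72% | 0.99 | 2% | 0.75 | 30% |
| 77% | 1.07 | 5% | 0.82 | 17% |
| 82% | 1.12 | 9% | 0.89 | 10% |
| 90% | 1.19 | 18% | 0.98 | 4% |

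Here the true HR is the one in shared responders. If the extra responders relapse at four times that rate, the apparent HR under no effect is 1.16, 1.30 and 1.51 at CR of 77%, 82% and 90%. If they relapse at the same rate and there is no effect, it stays at 1.00. Distortion therefore needs two things together: unequal CR rates and a different relapse rate in the extra responders.

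**Analysis sets side by side.** Protocol 8.1.6.2: "DOR and DOCR per IRF will be analyzed based on the ITT population". SAP 2.3 names the response-evaluable population for duration of response. SAP 5.8.4.7 names the responders within ITT. Because the protocol also defines both durations only in confirmed responders, its ITT wording does not bring non-responders into the comparison.

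**The case against.** The strongest reply is that nothing in the trial's decision depends on these analyses. Formal decision rules cover mPFS and then OS (SAP 3.2). DOR, DOCR and DFS are ungated. mPFS, OS and EFS are analyzed in ITT, conventional PFS is already planned as exploratory (SAP 5.8.2.2), and Kaplan-Meier estimates with CIs already come with the OS method. All of this stands, and it limits the point to removing or relabelling three comparisons.

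The illustrations can also be challenged. The 70% CR rate lies just below the protocol's cited range, and 70% × 88% = 61.6% relapse-free in CR compares with an assumed 2-year ABVD mPFS of 73% (SAP 5.1). At a 2-year horizon, about 11 of the 30 non-CR percentage points would have to stay event-free. The largest simulated errors need an 18-point CR gain, while the design assumes an 8-point mPFS gain. This stands too: the numbers show a mechanism and do not forecast its size.

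A reader might infer that the objectives themselves rule out a test, because one reads "To determine the DOR and duration of complete remission (DOCR) obtained in the A+AVD and ABVD arms" and makes no claim of improvement. The documents do not support that. The EFS objective has the same form, its ITT comparison is sound, and SAP 3.1 says secondary hypotheses will be tested.

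**Conclusion.** The concern holds as a caution of low consequence. The plan makes non-randomized between-arm comparisons of DOR, DOCR and DFS without saying so. They can hide or create a difference if the CR rate differs by arm and the extra responders have a different prognosis. With equal CR rates the distortion is expected to be small. Size and direction cannot be derived from the documents. Under the assumptions shown, a true ratio of 0.67 appears as about 0.74-0.90.

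Two stronger readings are tempting and go too far. One is that the hazard ratio and p-value can never reflect a treatment effect. That is too categorical, since the simulation recovers the true value when CR rates are equal and the same patients respond. The other is that the trial's main result is at risk. It is not, because mPFS and OS are compared in all randomized patients.

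**What to change.** In SAP 5.8.4.1, exclude DOR, DOCR and DFS from the log-rank and Cox comparison. Report Kaplan-Meier estimates with 95% CIs per arm, labelled descriptive. At minimum, label any hazard ratio descriptive, with no p-value and no treatment-effect claim. Keep between-arm inference with the ITT endpoints: mPFS, OS and EFS, with PFS exploratory.

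Protocol 8.1.6.2 prescribes the same analyses, so the change is a departure from the protocol. Protocol 8.1 requires departures to be indicated in the SAP, and SAP section 6 currently lists none, so an entry is needed there. In the same edit, settle on one analysis set for DOR and DOCR across protocol 8.1.6.2 (ITT), SAP 2.3 (response-evaluable, for duration of response) and SAP 5.8.4.7 (responders).

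The cost is SAP wording, a section 6 entry and the loss of p-values for three endpoints outside the testing hierarchy. No new data, sample size change or alpha change is needed.

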5.8.4.2 Complete Remission Rate at the End of Randomized Regimen per IRF

CR rate per IRF is defined as the proportion of patients who achieve CR at the end of treatment with randomized regimen (ABVD or A+AVD) as determined by an IRF.

The number and percentage of patients who experienced a CR at the end of treatment with ABVD/A+AVD will be summarized by treatment groups. The response rates between the 2 treatment groups will be tested using Cochran-Mantel-Haenszel (CMH) chi-square test, stratified by the stratification factors (Section 5.2). The CMH chi-square p-value and the relative risk (and odds ratio), along with its 95% 2-sided CI will also be provided. In

**Brentuximab vedotin (ADCETRIS™)
Statistical Analysis Plan, Study C25003**

addition, the absolute treatment difference in CR response rates will be provided along with the 95% 2-sided CI.

In addition, a logistic regression model will be used to further evaluate the treatment effects on CR rate after adjusting for some prognostic factors. Besides treatment and the stratification factors (Section 5.2), the following prognostic factors will be included in the model simultaneously: age, race (white, non-white), baseline ECOG score, baseline cancer stage, baseline B symptoms, and PET results from Cycle 2. The odds ratio and its associated 95% CIs will be presented. Subgroup analyses may be performed using subgroups defined for mPFS analyses. Additional exploratory analyses may be performed if deemed necessary.

In the primary analysis of CR using ITT population, nonevaluable patients will be treated as nonCR. Sensitivity analyses for CR per IRF will be performed using the response-evaluable population. CR rate per investigator will also be analyzed similarly using the ITT population.

5.8.4.3 Complete Remission Rate at the End of Frontline Therapy

CR rate at the end of frontline therapy per IRF is defined as the proportion of patients who achieve CR at the end of frontline therapy as determined by an IRF. CR at the end of frontline therapy is a binary outcome variable.

5.8.4.4 Event-Free Survival

EFS is defined as the time from randomization until any cause of treatment failure: disease progression, premature discontinuation of randomized treatment for any reason, or death due to any cause, whichever occurs first. EFS is a time-to-event variable.

5.8.4.5 Disease-Free Survival

DFS is defined as the time from CR to disease progression or to death from lymphoma or acute toxicity from treatment. Analyses of DFS will be performed based on the subset of the ITT population achieving a CR. DFS is a time-to-event variable.

5.8.4.6 Overall response rate

Overall response rate (ORR) is defined as the proportion of patients who achieve CR or PR at the end of treatment with randomized regimen (ABVD or A+AVD) as determined by an IRF.

ORR is a binary outcome variable.

5.8.4.7 Duration of Response (DOR) or Complete Response (DOCR)

DOR in subjects with confirmed response is the time between first documentation of response (PR or CR) and disease progression. DOCR in subjects with confirmed CR is the time between first documentation of CR and disease progression. DOR and DOCR per IRF will be analyzed based on the subset of ITT population who had response. DOR and DOCR are time-to event-variables.

5.8.4.8 PET Negativity Rate

PET negativity rate at Cycle 2 is defined as the proportion of patients with negative Cycle 2 PET results. PET negativity is a binary outcome variable.

5.8.5 Other Efficacy Endpoints

Alive without HL rate at 3 years and 5 years is defined as the proportion of patients who are alive without classical Hodgkin lymphoma at 3 years or 5 years after the patient's randomization date.

Alive without HL rates between the 2 treatment arms will be compared using a stratified Cochran-Mantel-Haenszel (CMH) test.

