#### **8.1.6.3 Exploratory Endpoints**

Alive without HL rate at 3 years and 5 years is defined as the proportion of patients who are alive without classical Hodgkin lymphoma at 3 years or 5 years after the patient's randomization date.

Alive without lymphoma rates between the 2 treatment arms will be compared using a stratified Cochran-Mantel-Haenszel (CMH) test.

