5. STATISTICAL METHODOLOGY

In general, summary tabulations will be presented that display the number of observations, mean, standard deviation, median, minimum, and maximum for continuous variables, and the number and percent (of non-missing) per category for categorical data, unless specified otherwise.

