5.4 Data Handling

5.4.1 Methods for Handling Missing Data

All available efficacy and safety data will be included in data listings and tabulations. Data that are potentially spurious or erroneous will be examined under the auspices of standard data management operating procedures.

In general, missing data will be treated as missing and no data imputation will be applied, unless otherwise specified. For Quality of Life Data, missing elements may be substituted with the average of non-missing items per published methods of analysis.

Last observation carried forward method and multiple imputation method may be considered for some clinical outcomes as deemed appropriate.

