5.8 Efficacy Analyses

All efficacy evaluations will be conducted using the ITT population unless otherwise specified.

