5.8.2 Primary Efficacy Analysis

Final analysis of mPFS will be performed when 260 mPFS events have been observed, which is estimated to occur by 24 months after the last patient is randomized.

Stratified log-rank testing will be used to compare mPFS between the 2 treatment arms as the primary analysis. The stratification factors include region and number of IPFP risk factors at baseline (Section 5.2). The hazard ratios along with the 95% confidence interval (CI; 2-sided) will be estimated using the stratified Cox model with treatment as the explanatory variable. The Kaplan-Meier (K-M) survival curves and survival probability at 2 and 3 years along with the 2-sided 95% CIs will also be provided for each treatment group.

In addition, a stratified Cox regression model will be used to further evaluate the treatment effects on mPFS after adjusting for some prognostic factors. Besides treatment and the stratification factors (Section 5.2), the following prognostic factors will be included in the model simultaneously: age, race (white, non-white), baseline ECOG score, baseline cancer

Brentuximab vedotin (ADCETRIS™)
Statistical Analysis Plan, Study C25003

stage, baseline B symptoms, and PET results from Cycle 2. Additional exploratory analyses may be performed if deemed necessary.

For patients with mPFS events, the reasons leading to the determination of mPFS will be tabulated. For patients without mPFS events, the main reason for censoring will also be tabulated.

The proportional hazard assumptions will be examined and sensitivity analysis may be conducted if appropriate.

5.8.2.1 mPFS Sensitivity Analyses

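### The exploratory 3- and 5-year alive-without-HL rates are crude proportions with no endpoint-specific rule for unknown status; under the SAP's general defaults the 5-year rates come out about 1 to 4 points low if dropout is unrelated to prognosis and every patient can reach 5 years.

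*SAP*

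**What the plan says.** **The endpoint.** SAP 5.8.5 and protocol 8.1.6.3 define the rate as the proportion of patients alive without classical HL 3 or 5 years after randomization. The SAP adds "Alive without HL rates between the 2 treatment arms will be compared using a stratified Cochran-Mantel-Haenszel (CMH) test". The protocol has "Alive without lymphoma rates between the 2 treatment arms will be compared using a stratified Cochran-Mantel-Haenszel (CMH) test". Protocol 3.3 lists the endpoint as exploratory.

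**Text that bears on unknown status.**
- SAP section 5, on summaries in general: "number and percent (of non-missing) per category for categorical data, unless specified otherwise".
- SAP 5.4.1: "In general, missing data will be treated as missing and no data imputation will be applied, unless otherwise specified". The same section adds "Last observation carried forward method and multiple imputation method may be considered for some clinical outcomes as deemed appropriate", which commits to neither method.
- SAP 5.8: "All efficacy evaluations will be conducted using the ITT population unless otherwise specified".
- SAP 5.8.4.2, for CR at the end of the randomized regimen only: "nonevaluable patients will be treated as nonCR". SAP 5.8.4.1 extends the CR methods to the other secondary binary endpoints. The alive-without-HL rate sits outside that group, in 5.8.5.

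**Related analyses that handle censoring.** For mPFS, SAP 5.8.2 states that Kaplan-Meier curves and "survival probability at 2 and 3 years along with the 2-sided 95% CIs will also be provided". SAP 5.8.2.2 applies similar methods to PFS and adds a mixture cure model with a cured fraction per arm.

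**Length of follow-up.** Protocol 4.1 and 7.10, and parts of 4.3 and 7.6, support 5 years of follow-up for all. The Protocol Summary (Duration of Study) and other parts of 4.3 and 7.6 put closure at about 7 years in total, or about 4 years after the last patient is randomized.

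**The concern.** A proportion at a fixed time treats status at that time as fully observed, but the plan's own sample-size assumptions include 5% annual dropout. Under the general defaults, a patient of unknown status leaves both numerator and denominator. That exclusion is not neutral. A patient who fails in year 1 and would have dropped out in year 3 is kept as a known failure. A patient who is HL-free and drops out in year 3 is removed. Failures are therefore over-represented and the rate is too low, provided dropout is unrelated to prognosis.

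The definition is also open on one point that sets the size of the bias: whether a patient who relapses and is back in remission after salvage counts as alive without HL. The wording reads most naturally as current status, and protocol 7.10 allows status after progression to be collected by phone, but neither document says so.

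At stake are the absolute 3- and 5-year rates, which readers would quote as long-term disease control. The trial's confirmatory conclusions are not at stake.

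**Working it through.** **The plan's own figure.** The documents give no figure for this endpoint, so I checked the planning figures used as inputs. ln(0.81)/ln(0.73) = 0.670, matching HR 0.67. Schoenfeld events: 4 × (1.960 + 1.282)² / (ln 0.67)² = 262.1, so 263 against the stated 260; power at 260 events is 89.8%. The inputs reproduce.

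**Inputs from the documents.** 2-year mPFS 81% (A+AVD) and 73% (ABVD), 5% annual dropout and 36 months of accrual (SAP 5.1); 5-year OS 91% and 88% (protocol 8.1.6.2).

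**Assumed.** After year 2 the hazard is 10% of its earlier value (the documents give a plateau but not its size). Dropout is exponential and independent of prognosis, λ = −ln 0.95 = 0.0513. Every patient can reach 5 years.

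**Formula, unknowns left out.** Rate = S(5)G(5) / [S(5)G(5) + F]. S is the true HL-free probability, G(5) = 0.95⁵ = 0.7738, and F is the probability of a failure seen before dropout.

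**Reading 1: first relapse or death is a permanent failure (mPFS rates as proxy).** With h = −ln(S(2))/2 and h₂ = 0.1h:

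F = h/(h+λ) × [1 − e^(−2(h+λ))] + S(2)G(2) × h₂/(h₂+λ) × [1 − e^(−3(h₂+λ))]

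- A+AVD: h = 0.1054, S(5) = 0.7848, S(5)G(5) = 0.6073, F = 0.2020. Rate = 0.6073/0.8093 = 75.0% against a true 78.5%: 3.4 points low.
- ABVD: h = 0.1574, S(5) = 0.6963, S(5)G(5) = 0.5388, F = 0.2855. Rate = 0.5388/0.8243 = 65.4% against a true 69.6%: 4.3 points low.
- Unknown share: 1 − 0.8093 = 19% and 1 − 0.8243 = 18%.
- At 3 years: 78.5% against 80.2% (1.7 low) and 69.7% against 71.9% (2.1 low).
- With a full plateau the 5-year bias is 3.4/4.3; with no plateau 3.5/3.6.
- mPFS also counts treated non-CR, so it overstates failures here. With 70–85% of the hazard the bias is 2.7–3.1/3.5–3.9.

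**Reading 2: current status, with only death absorbing.** Let d = −ln(5-year OS)/5 and F = d/(d+λ) × [1 − e^(−5(d+λ))], and let q be the share of survivors who are HL-free (assumed 80–100%). Then rate = q·S·G/(S·G + F).

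- A+AVD: 0.7041/(0.7041 + 0.0795) = 89.85% × q against 91% × q: 0.9 to 1.2 points low.
- ABVD: 0.6809/(0.6809 + 0.1061) = 86.5% × q against 88% × q: 1.2 to 1.5 points low.
- A simulation with 30–50% of relapses salvaged (assumed) gave 1.0–1.2/1.2–1.4.

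**Arm difference at 5 years, Reading 1.**

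| Handling of unknowns | A+AVD | ABVD | Difference |
|---|---|---|---|
| True | 78.48 | 69.63 | 8.85 |
| Left out | 75.04 | 65.37 | 9.67 (+0.82) |
| Counted as failures, S(5)G(5) | 60.73 | 53.88 | 6.85 (−2.00) |

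**If the study closes 4 years after the last patient.** With uniform 36-month accrual, one third of patients cannot reach 5 years. If they are kept only when they fail, the 5-year rates are 11.6/13.8 low under Reading 1 and 4.9/6.0 low under Reading 2 (40% salvaged). Restricting to patients past their anniversary removes this extra bias.

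**If dropout depends on prognosis.** Under Reading 1, if eventual failures drop out twice as fast before failing, the bias shrinks to 2.3/2.9 low; the sign reverses at about 4.3–4.4 times. Under Reading 2, if dropout doubles after relapse, the bias is about 0.1; at four times, rates are 1.6/2.1 too high.

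**The case against.** The strongest case against runs as follows.

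- **The plan is not silent.** SAP 5 and 5.4.1 give general defaults that reach this endpoint. That stands: what is missing is an endpoint-specific rule, and the defaults are what produce the bias.
- **Counting unknowns as failures is a weak reading.** A reader might infer from the ITT statement that unknowns are failures, which would put the 5-year rates 15.7 to 17.8 points low. The ITT statement fixes who is analysed and in which arm; it does not classify unknowns. Where the sponsor wanted that rule, for CR, it was written out. Those figures should not be presented as the plan's expected result.
- **The 5% dropout is borrowed.** It is a sample-size assumption for mPFS, not a forecast of unknown status at 5 years. Phone contact and database searches could lower the unknown share, and it could also be higher. That stands, so the sizes are illustrative.
- **Other analyses cover long-term control.** The Kaplan-Meier analyses of mPFS and PFS and the mixture cure model all handle censoring. That stands and limits the harm, although the named Kaplan-Meier time points stop at 3 years.
- **The effect on the comparison is negligible.** A shift of 0.8 points compares with a sampling half-width of about 4.9 points for the difference (620 per arm). That stands when unknowns are left out.
- **The follow-up conflict is a separate matter.** In part. It is a protocol inconsistency in its own right, but it also decides whether a 5-year rate can be observed for everyone.

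**Conclusion.** The concern holds as a minor point. Following the SAP's general defaults gives 5-year rates that are about 3 to 4 points low if first relapse or death is a permanent failure, and about 1 point low if current status counts. This rests on 5% annual dropout unrelated to prognosis, 5 years of potential follow-up for every patient, and the assumed post-2-year hazard and salvage share. The direction is not guaranteed: strongly prognosis-related dropout would reverse it.

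Three stronger conclusions might be drawn, and the documents do not support them:
- That the comparison is invalid. With equal censoring the CMH test remains valid under the null, and with unknowns left out the arm difference moves by under 1 point.
- That the bias is 5 to 14 points. That needs closure 4 years after the last patient and also late entrants kept only when they fail. The plan specifies no such handling, and its follow-up statements conflict.
- That the primary or key secondary conclusions are affected. They are not.

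**What to change.** In SAP 5.8.5 and protocol 8.1.6.3:

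1. State whether a patient back in remission after salvage counts as alive without HL.
2. If not, replace the proportion and CMH test with Kaplan-Meier estimates at 3 and 5 years and a stratified difference with 95% CI. This extends the planned PFS analysis to 5 years.
3. If so, restrict to patients whose 3- or 5-year anniversary precedes data cut-off, and name multiple imputation based on relapse history and follow-up time.
4. Report the number with unknown status per arm, because both options still assume that dropout is unrelated to prognosis given the data used.
5. Reconcile the follow-up statements in the Protocol Summary (Duration of Study) and protocol 4.1, 4.3, 7.6 and 7.10.

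The cost is wording and one program, with no new data. Under option 2 the 5-year intervals are no wider than those with unknowns left out: 95% half-widths of about 3.4/3.8 points against 3.8/4.1 (A+AVD/ABVD, 620 per arm, full follow-up). Under option 3 they widen if the study closes 4 years after the last patient, because about a third of patients leave the 5-year analysis.
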